## Study Overview

**STUDY TITLE:** Dopaminergic enhancement of rehabilitation therapy early after stroke

**INSTITUTIONAL REVIEW BOARD (IRB) #:** 22-000104

**DESCRIPTION:** Telerehabilitation (TR) is defined as delivery of rehabilitation services via communication technologies. This study uses an established TR system and protocol to supplement usual care, and also asks whether adding a dopaminergic drug enhances TR effects. In addition, the predictive value will be examined for two biomarkers that characterize capacity for brain plasticity.

Patients with arm weakness due to a new stroke in the past 30 days will be randomized to receive [1] 6 weeks of TR + Sinemet 25/100 once/day, on top of usual care (UC), [2] 6 weeks of TR + placebo once/day, on top of UC, or [3] UC alone. TR consists of 70 minutes/day of activity targeting upper extremity (UE) function, delivered in the home and (when appropriate) initiated in the inpatient rehabilitation facility (IRF) setting. Two previously validated predictive biomarkers are hypothesized to prospectively identify treatment responders: first, extent of stroke-related injury to the corticospinal tract (CST), obtained via MRI scan; and second, a polygene score focused on dopamine neurotransmission.

The currently planned study uses very similar software and hardware as the TR system as in a prior national study that found that this TR system was safe, associated with significant gains in arm function and in global function, and had efficacy comparable to that seen when the same dose of therapy was delivered in the clinic (i.e., delivered in the same manner as standard care). In that prior study, the FDA determined (Q140628) that the investigation was a non-significant risk device study.

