(6% vs. 3%), a fact that is clearly noted in the informed consent form (ICF). Key concerns exist with the design of this study, concerns that limit interpretation of non-efficacy outcomes. First, the target population was not well defined, as this study enrolled patients with any deficit, of almost any severity, as long as gait was not independent; furthermore, the diagnosis of stroke was based entirely on clinical findings. Second, provision of concomitant physical therapy frequently did not follow study protocol. Third, the timing of pill ingestion relative to physical therapy was variable (e.g., the study drug was not taken per protocol in 45% of therapy sessions). Such details are critically important to trials of stroke recovery, and so perhaps the strongest message from this trial was that Sinemet 25/100 is safe early after stroke.

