## Randomize the patient

Using a web-based randomization procedure, the patient will be randomized into one of three treatment groups:

- **TR + Sinemet:** Patients in this group will receive 36 therapy sessions targeting arm motor function starting as soon as possible after randomization (target is next day). This therapy is structured as 6 weeks of TR, 6x/week, for 6 weeks. Up to 8 weeks are permitted to make up for lost sessions to achieve 36 sessions in which >50% of assigned minutes are completed by the patient. For the first 18 sessions (approximately the first 3 weeks), the patient will take their study pill (Sinemet 25/100) 1-2 hours after breakfast or lunch, then 1 hour later begin their 70-min TR session. TR+Sinemet is in addition to UC (i.e., the patient is to continue all therapies and medication provided as part of standard medical care).
- **TR + placebo:** Patients in this group will receive 36 therapy sessions targeting arm motor function starting as soon as possible after randomization (target is next day). This therapy is structured as 6 weeks of TR, 6x/week, for 6 weeks. Up to 8 weeks are

permitted to make up for lost sessions to achieve 36 sessions in which >50% of assigned minutes are completed by the patient. For the first 18 sessions (approximately the first 3 weeks), the patient will take their study pill (placebo) 1-2 hours after breakfast or lunch, then 1 hour later begin their 70-min TR session. TR+placebo is in addition to UC (i.e., the patient is to continue all therapies and medication provided as part of standard medical care).

- **Usual care (UC):** Patients in this group will not receive TR or a blister pack of study pills. Instead, each will receive UC (i.e., will continue all therapies and medication provided as part of standard medical care). In order to maximize participant retention, patients in this group will be offered a 6-week course of TR after Visit 4 (i.e., 5-6 months after stroke). At the end of their TR therapy, at the time that their TR system is picked up from their home, the therapist will perform ARAT, FMA-UE, BBT, NHPT, and mRS in the patient's home.

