## TR Therapy

### The telerehabilitation intervention

**Summary:** Patients are assigned 70 minutes of telerehabilitation (TR) therapy each day, 6 days/week, for 6 weeks, targeting the paretic UE. Functional games and exercises comprise 65 of these daily minutes, and 5 minutes/day is spent on stroke education (which requires targeted arm movement).

Therapy must begin within 7 days of randomization. The first TR session will be a supervised session, whether in-person or via videoconference.

TR is delivered over 36 sessions, each 70-minutes in duration. Of these, 18 sessions are supervised by a licensed OT or PT; for patients receiving TR while admitted to Cal Rehab, the therapist may be in the same room as the patient or communicate via videoconference, and for patients who are at home, the therapist is present via videoconference. The other 18 sessions are unsupervised (i.e., no OT or PT is present at any time during the session; for inpatients at Cal Rehab, the therapist can sit near the patient, with minimal interaction, at the therapist's judgment). Ideally, a given patient will work with the same therapist for the entire 6 weeks. To accommodate possible external events (e.g., illness or family reasons), patients are permitted up to 8 weeks to complete these 36 treatment sessions. In the prior national trial, the FDA determined (Q140628) that the investigation using an earlier generation of the same device was a non-significant risk device study. The FDA made the same determination (Q212693) for the current study. When possible, patients begin TR each day at the time indicated in the behavioral contract. Patients are free to pause between games and activities, as needed. Patients are also instructed to perform all UC that is provided to them—enrollment in this TR study does not interfere with any treatment provided as part of standard of care. A session is considered completed when the patient has completed >50% of the assigned 70 minutes by midnight. After the 36 treatment sessions are completed, or if that does not happen then at the end of 8 weeks, the team retrieves the TR system from the patient's home.

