## Visit 5 (for UC only)

As previously mentioned, patients in the UC group will be offered a 6-week course of TR after Visit 4 (i.e., 5-6 months after stroke). For those subjects who choose to complete this training, the same assessments administered at Visit 4 will be re-assessed at Visit 5. These include the following:

- ARAT
- BBT
- mRS
- FMA-UE
- NHPT
- SIS—ADL and hand subsections
- The patient will be asked about interval medical history and AEs

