### Statistical Analysis

We will present descriptive statistics by group for the important covariates including age, site, time from stroke to randomization, MEP status, and hours of outside rehabilitation. We will also report compliance, defined as the percentage of the 36 sessions during which patients complete more than half ( $\geq 36$  min) of assigned activities. For all analyses, data not normally distributed will be appropriately transformed.

Primary efficacy analysis will use the Intent-To-Treat population, consisting of all randomized subjects and multiple imputation for missing data. Secondary analysis will examine the Per-Protocol population, defined as all subjects with complete data who complete  $\geq 36$  minutes of assigned activities on  $\geq 30$  of the 36 therapy sessions over no more than 8 weeks. Analyses will be performed using SAS and R software.

Logistic regression will be used to create a propensity score for treatment group using age, time from stroke to randomization, and total hours of outside rehabilitation therapy from Visit 1 to Visit 4 (or Visit 3 when change is to visit 3). Inverse weights based on this score will be used in secondary analyses to compute adjusted change distributions and corresponding p values. The primary analyses will be based on the inverse propensity score weighted (adjusted) change from base. The corresponding unadjusted changes will also be reported as a secondary analysis. Since this is a randomized trial, we expected the primary propensity adjusted and unadjusted results to be similar.

**Aim 1. TR+UC is superior to UC alone:** A 6-week program of TR targeting arm movement added to UC will result in better arm function as compared to UC alone. The primary endpoint is the change in ARAT score from baseline to 1 month after end of therapy (Visit 4).

The mean differences in ARAT score change from Visit 1 (baseline) to Visit 4 (1 month after end of therapy) will be compared on the log scale using an inverse propensity adjusted t test. A similar method will be used for the secondary change from Visit 1 to Visit 3 (end of therapy). We will first compare the combined TR + UC groups versus the UC group (Aim 1) and then compare TR+Sinemet+UC versus TR+placebo+UC under this model. (Aim 2). As a secondary analysis, we will report the corresponding unadjusted results.

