**Aim 2. TR+Sinemet is superior to TR+placebo:** Among patients randomized to TR, gains in arm function will be greater in those who take Sinemet (25/100) prior to daily TR, as compared to patients who take placebo prior to TR.

The above analyses will be repeated but instead comparing patients randomized to [1] TR+Sinemet vs. [2] TR+placebo.

**Aim 3. Less CST injury and higher dopamine polygene score predict better recovery of arm function:** Across all subjects, change in arm function will be highest in those with lower % CST injury and in those with higher dopamine polygene scores. These relationships will remain significant when examining only patients randomized to TR. The drug X gene score interaction term will be significant such that the slope of arm gains in relation to the polygene score will be smaller (less steep) in those receiving Sinemet.

**H3A:** Using linear regression, we will test whether lower % CST injury predicts higher change in ARAT score from Visit 1 to Visit 4, after controlling for baseline ARAT score and clinical measures (age, time from stroke to randomization, and total hours of outside rehabilitation therapy from Visit 1 to Visit 4). Primary analysis will examine all enrollees. Secondary analysis will examine this relationship separately for patients randomized to one of the two TR groups, while tertiary analysis will examine this separately across all three treatment groups.

Restricted cubic splines will be used to determine if the effect of continuous covariates such as age are linear. A linear model that includes individual clinical measures will be used rather than propensity adjustment so that the effect of % CST injury can be compared to the effects of the other covariates. This approach also allows us to test the hypothesis that % CST injury predicts ARAT gains beyond what can be learned from clinical variables alone.

**H3B:** We will test whether higher dopamine polygene score predicts higher change in ARAT score from Visit 1 to Visit 4, after controlling for the same covariates as in H3A. Analyses will follow those described in H3A.

Secondary analysis will repeat H3A and H3B using change in BBT from Visit 1 to Visit 4 as the dependent measure. Tertiary analyses will repeat these methods focusing on change in FMA-UE, CES-D, mRS, NHPT, SIS-ADL, and SIS-hand scores.

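### The Per-Protocol rule counts only telerehabilitation sessions: as written it admits no usual-care patient for Aim 1 and ignores pill intake for Aim 2

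*Combined protocol and SAP*

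**What the plan says.** The Statistical Analysis section makes Intent-To-Treat primary and adds: "Secondary analysis will examine the Per-Protocol population, defined as all subjects with complete data who complete" at least 36 minutes of assigned activities on at least 30 of the 36 therapy sessions, over no more than 8 weeks. No arm is exempted and no separate UC rule is given.

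The 36 sessions are the TR course. Under The telerehabilitation intervention: "A session is considered completed when the patient has completed >50% of the assigned 70 minutes by midnight". The reported adherence measure has the same basis: "We will also report compliance, defined as the percentage of the 36 sessions during which patients complete more than half" of the assigned activities.

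On UC, Randomize the patient states: "Patients in this group will not receive TR or a blister pack of study pills". A footnote to the Schedule of Events confirms that only the TR groups have the six weeks of training. UC patients get TR later, if at all: "patients in the UC group will be offered a 6-week course of TR after Visit 4".

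For Aim 2 the plan says: "The above analyses will be repeated but instead comparing patients randomized to" TR+Sinemet or TR+placebo. It gives no separate Per-Protocol definition for that comparison.

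**The concern.** One rule serves two different comparisons and fits neither as written.

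Aim 1 compares the two TR arms combined with UC. A membership rule based on TR sessions cannot be met by a patient who has no TR before the endpoint. Someone must therefore decide, outside the plan, how UC patients enter the set. The natural decision is to admit them on complete data alone. That compares TR patients selected on adherence with UC patients who are not, and the plan does not label it so.

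Aim 2 is a drug comparison. Its only adherence-based analysis set takes no account of whether the drug was taken. The Background section treats drug intake as important: it criticises an earlier levodopa trial because "the timing of pill ingestion relative to physical therapy was variable", and gives as its example that drug was not taken per protocol in 45% of sessions.

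At stake are the named secondary analysis for both treatment aims and the chance that its membership rule is settled after data have been seen.

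**Working it through.** **The plan's own figure.** Sample Size gives a difference of 5.7, SD 7.4, two-sided alpha 0.05, 80% power and 27/27/18 patients, so 54 TR against 18 UC.
- UC patients needed = (1 + 1/3) × (1.960 + 0.842)² × (7.4/5.7)² = 1.333 × 7.849 × 1.685 = 17.6, so 18. Total 4 × 18 = 72, as stated.
- Power at 18 against 54 is 0.81 by the normal approximation and 0.80 by the t distribution.

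The sample size is sound. The problem lies only in the definition of the set.

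**Aim 1, rule as written.**
- TR sessions available to a UC patient before Visit 4: 0. Sessions required: 30.
- Qualifying UC patients: 0 of 18. The contrast cannot be estimated.
- A UC patient who accepts deferred TR could reach 30 sessions, but only after the primary endpoint.

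**Aim 1, session rule for the TR arms only.** The contrast can then be estimated. With nobody excluded it is 18 against 54, power 0.81. If, for illustration, every arm lost the 20% that Sample Size gives as the possible dropout, it is 14.4 against 43.2, power 0.72 (normal) or 0.70 (t), before any session-rule exclusions.

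**Aim 2, pill intake.** Session completion, compliance and Per-Protocol membership all count minutes of TR activity. None counts pills. A patient with 0 of 18 pills and 30 completed sessions therefore qualifies.

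Assume a zero-intake patient has no drug effect. With k such patients among n qualifying Sinemet patients, the expected contrast is multiplied by 1 − k/n. For k = 1:
- n = 27 (all qualify): 1/27 = 3.7% dilution.
- n = 21 (27 × 0.80 = 21.6, rounded down): 1/21 = 4.8%.

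The documents give no basis for k.

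**Denominator for an intake criterion.** The session rule already uses 30/36 = 5/6. Applied to 18 scheduled pills, 5/6 is 15. The denominator is not described consistently, however. Study Overview and the Aim 2 statement describe once-daily Sinemet alongside six weeks of TR and before each day's TR. Randomize the patient and Dispense Study Medication describe 18 pills for the first 18 sessions. Those last two sections also differ on meal timing: 1–2 hours after breakfast or lunch in one, an hour after in the other.

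**The case against.** The best reply on Aim 1 is that the empty comparator is a drafting slip. The 36 sessions are plainly TR sessions, nobody would apply them to UC, and one clause cures it. That is right about intent, and a reader who inferred that the sponsor planned an analysis without controls would go too far. It remains true that the clause is missing and that the definition is worded for all subjects.

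Selection on adherence is also inherent in Per-Protocol sets, and this one is already secondary. That stands too. A reader might go on to infer a bias of known size. The documents do not support one. It would need a correlation between adherence and ARAT change, and the plan gives none. It would also need the share of TR patients who meet the session rule here. The 98.3% TR compliance in Background comes from a trial that enrolled later after stroke. Incomplete data cannot be counted as selection peculiar to TR, because complete data are required of all subjects. The planned test is on the log scale besides.

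On Aim 2, the pill is tied to the session, since TR starts an hour after it, so patients who attend may mostly take it. The 45% figure belongs to another trial and is no forecast for this one. CRFs are mentioned but not supplied, so it cannot be said that intake goes unrecorded. All of this limits the likely size of the problem. It does not supply the missing criterion.

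Finally, the two operational sections agree on 18 pills over 18 sessions. A reader might work out intake against 36 sessions or 42 days and conclude that full adherence is impossible. With 18 pills dispensed, those are not working denominators. The differing descriptions are a wording conflict for the sponsor to reconcile, not evidence of poor adherence.

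**Conclusion.** The concern holds as a gap in a secondary definition and should be fixed. For Aim 1, the rule as written admits 0 of 18 UC patients. Under the likely intended reading the contrast can be estimated but is selected on one side, and neither the size nor the direction of any resulting bias can be derived from the documents. For Aim 2, the set takes no account of pill intake. Each zero-intake Sinemet patient retained costs about 3.7% of the contrast if all 27 qualify, assuming no drug effect without intake. How many there will be is unknown, so the total dilution could be nil.

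A reader might infer that the trial's main result is threatened. It is not: the primary analysis is Intent-To-Treat, its population is defined separately, and the sample size reproduces.

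**What to change.** Define Per-Protocol by aim and arm.

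- **All arms:** keep the complete-data requirement, and state it for the endpoint and visit being analysed (ARAT, BBT and the others; Visit 3 or Visit 4).
- **Aim 1:** apply the session rule to the two TR arms only; UC patients qualify on complete data. Report the result as supportive of Intent-To-Treat, with the share of TR patients excluded. This discloses the selection but does not remove it.
- **Aim 2:** require the session rule plus a pill-intake criterion over the sessions for which pills are scheduled, and name the data source. The sponsor should set the threshold before outcomes by pill group are examined; this matters because the Blinding section leaves the study statistician unblinded to pill type. The 5/6 share already used for sessions is one example.
- **Before that:** reconcile Study Overview and the Aim 2 statement with Randomize the patient and Dispense Study Medication on the pill period, and the last two with each other on meal timing, so that the intake denominator is defined.

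The cost is SAP wording, a pill-intake record if the CRFs do not already hold one, and possibly a smaller Aim 2 Per-Protocol set. The Intent-To-Treat analysis and the sample size do not change.

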## Dispense Study Medication

Study medication will be dispensed at Visit 1, or shortly after. Patients randomized to the TR+Sinemet and the TR+placebo groups will be given a blister pack of 18 pills with instructions to take one pill an hour after breakfast or lunch 6 days/week for the first 18 sessions (approximately the first 3 weeks). TR will begin 1 hour after pill ingestion. Patients will be given apple sauce to take with their pill as needed, following dysphagia restriction guidelines, to mitigate concerns for potential nausea. As needed, patients may also be provided with an antacid drug. Patients in the UC group will not be given a blister pack of study pills or apple sauce.

The UCLA Pharmacy will generate the two types of study pills (i.e., Sinemet 25/100 and placebo). These two pills will be indistinguishable internally and externally (i.e., the internal powder will be the same color, and the external over-encapsulation will be identical), across both pill types. Pills will be organized into an 18-pill blister pack.

In patients with stroke, oral Sinemet 25/100 once/day is not associated with increased risk or with decreased acceptability of risks For this reason, the current study does not need to be conducted under an investigational new drug application to the FDA.

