## Therapist-facing software

We developed a therapist-facing web portal that treatment therapists use for treatment planning and patient monitoring. All treatment is generated and supervised by a licensed OT or PT. Therapists use a graphical interface to drag treatment elements (functional games, exercises, and stroke education) into a 70-min planner for each day's session; they then adjust the challenge level (games) and the duration (games and exercises) of each.

**Videoconferences:** For the supervised sessions that occur for patients who are living in their home, the treatment therapist joins the patient for 60 minutes of their session using HIPAA-compliant software (VSee; Sunnyvale, CA). Supervised sessions that occur while a patient is still admitted to Cal Rehab may have the therapist join the patient via VSee or live in the patient's room, per the therapist's judgment. During supervised sessions, therapists monitor therapy and provide patients with real-time positive feedback, answer questions, perform assessments, review treatment plans, and provide encouragement. Therapists also discuss how UE movements practiced during TR can be extended to become part of activity in the home. Any AEs and serious adverse event (SAEs) are reviewed. Note that 9.7% of patients receiving TR in the national trial had shoulder pain, and all patients could be helped by their therapist remotely, without pausing TR therapy. Therapists write an electronic clinic note after each videoconference, as standard good clinical practice.

The same therapist-facing web portal allows therapists to review, at any time, from any secure location:

Usage statistics: For games and for the stroke education module, we use the TR system's sensors--every game click, tap, squeeze, or shot is sent to the lab server in real time.

Performance data: We provide therapists with concise graphic readouts of scores on each game, over time. In this way, therapists can monitor patient compliance and performance, and

then use their professional judgment to modify game/exercise choices and difficulty levels accordingly, at any time.

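### The per-protocol set for Sinemet versus placebo is defined only by telerehabilitation activity and has no pill criterion (low priority, secondary analysis only)

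*Combined protocol and SAP*

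**What the plan says.** The per-protocol population is defined once, in the Statistical Analysis section before the aims are taken up: "Secondary analysis will examine the Per-Protocol population, defined as all subjects with complete data who complete" at least 36 minutes of assigned activity on at least 30 of the 36 sessions, in no more than 8 weeks. The same section states: "We will also report compliance, defined as the percentage of the 36 sessions during which patients complete more than half" of the assigned activities. Under The telerehabilitation intervention, "A session is considered completed when the patient has completed >50% of the assigned 70 minutes by midnight". All three rules are counted in telerehabilitation (TR) minutes or sessions.

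For Aim 2 the section says: "The above analyses will be repeated but instead comparing patients randomized to [1] TR+Sinemet vs. [2] TR+placebo". It defines no separate population.

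Patients in both TR arms receive an 18-pill blister pack. Under Randomize the patient, the TR+placebo entry matches the TR+Sinemet entry apart from the pill. Under Dispense Study Medication, "TR will begin 1 hour after pill ingestion".

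On recording, the Therapist-facing software section says of game use that "every game click, tap, squeeze, or shot is sent to the lab server in real time". The five daily items on the TR system are a motor test, a finger-tap test, shoulder pain, fatigue and perceived effort. The one weekly item about the pill, in Week 3, asks patients to guess which pill they had.

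**The concern.** A per-protocol analysis is read as the effect in patients who were treated as planned. For Aim 2 the treatment under test is the pill. The rule checks whether patients did their TR, which both arms receive alike, and does not ask whether they took the pill. If the drug works, Sinemet-arm patients who did not take it would stay in the set and pull the estimate toward zero.

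The protocol treats this issue as important. Its Background criticises an earlier levodopa trial because pill timing relative to therapy varied, with drug not taken per protocol in 45% of therapy sessions, and says such design concerns limit what can be concluded from that trial. Without intake and timing data, a null Aim 2 result here would be open to the same criticism. Half of the 36 sessions are unsupervised, so intake cannot be taken for granted.

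**Working it through.** **1. Does a patient with no pills qualify?** Take a TR+Sinemet patient with 0 of 18 pills who does at least 36 minutes on 30 sessions within 8 weeks and has all outcome visits.

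| Criterion | Refers to the pill? | Met? |
|---|---|---|
| Complete data | Not defined as including pill data | Yes |
| At least 36 minutes of assigned activity | No; minutes of the 70-minute TR session | Yes |
| At least 30 of 36 sessions | No; a session is completed on minutes alone | Yes |
| No more than 8 weeks | No | Yes |

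The rule asks for 30/36 = 83% of TR sessions and 0/18 = 0% of pills.

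**2. Does Aim 2 use this set?** The text does not say so in words. The population paragraph comes before all the aims, Aim 2 repeats the preceding analyses, and no other per-protocol set is defined. The inference is direct.

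**3. The plan's own figure.** Inputs from Sample Size: difference 5.7 points, SD 7.4, two-sided alpha 0.05, 80% power, 3:1 for combined TR versus usual care.
n(UC) = (1 + 1/3) × (1.960 + 0.842)² × 7.4² / 5.7² = 17.6, rounded up to 18. TR = 54 and the total is 72, as stated. This calculation is for Aim 1 and does not depend on the per-protocol rule.

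**4. Possible dilution (illustration only).** Assume no effect in non-takers, equal weights, and n patients in the Sinemet arm of the set. Then k non-takers remove k/n of the true contrast.
- n = 27 (everyone randomised): 1/27 = 3.7%; 3/27 = 11.1%; 5/27 = 18.5%.
- n = 22 (27 × 0.8 = 21.6, using the plan's 20% dropout ceiling with no extra enrolment and before any session-based exclusion): 1/22 = 4.5%; 3/22 = 13.6%; 5/22 = 22.7%.

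The second row is nearer to a realistic per-protocol count. The values of k are arbitrary, because the documents give no non-adherence rate for this trial and no Aim 2 effect size.

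**5. Precision cost of a pill criterion.** SE = 7.4 × √(2/n), raw ARAT points.
- n = 22: 2.23.
- n = 19 (3 fewer per arm): 2.40; √(22/19) = 1.076, about +8%.
- n = 17 (5 fewer per arm): 2.54; √(22/17) = 1.138, about +14%.

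The planned comparison is on the log scale with inverse propensity weights, so these figures indicate relative size and are not the analysis's own standard errors.

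**The case against.** The strongest reply is that little depends on this rule. The trial is powered for Aim 1 only, the primary population is intent-to-treat, and the per-protocol analysis of Aim 2 is secondary. That stands, and it sets the priority.

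A reader might infer that pill intake and timing go unmeasured. The documents do not support that. The case report forms were not supplied and the Schedule of Events table is partly lost. There are also contacts at which intake could be noted: 18 supervised sessions, a clinic note after each videoconference, and weekly questions on interval history and adverse events. None is stated to record the pill, but absence from the supplied text does not show that nothing is recorded. If the forms do record it, the definition still ignores those data.

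A reader might also infer that the Aim 2 result will be materially biased. That is not shown either, since 0 of 18 pills is a limiting case with no frequency behind it.

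Finally, selecting on pill intake after randomisation can unbalance the arms if tolerability differs. If the Background's vomiting rates of 6% versus 3% applied and every affected patient stopped the pill, that would be 0.06 × 27 = 1.6 versus 0.03 × 27 = 0.8 patients per arm, from vomiting alone. This stands as a reason to keep intent-to-treat primary and to show the result both ways. It does not defend the present rule, which already selects on behaviour after randomisation but on the component that does not differ between arms.

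**Conclusion.** The point holds for the secondary Aim 2 per-protocol analysis. As written, that analysis cannot be read as the drug effect in patients who took the drug as planned, because pill intake plays no part in the selection. This rests on the stated definition and on the direct inference that Aim 2 uses it. The size of any dilution is unknown; the 3.7% and 4.5% per non-taker are illustrations that assume no effect in non-takers. The point is low priority: no primary analysis changes, and neither Aim 1 nor the total of 72 is affected. It is still worth acting on early, because a cut-off can be written later but unrecorded daily intake and timing cannot be reliably recovered once patients have finished.

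**What to change.** For the secondary Aim 2 per-protocol analysis only:

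- Add a minimum number of pills, for example at least 15 of 18 (83%, matching 30 of 36), each taken before that day's TR session and within a stated window around the planned 1 hour. The cut-off and the window are judgements.
- Fix both now by amendment, before anyone sees outcome data by arm. A deadline tied to unblinding would not be enough, because the Blinding section says the study statistician already knows the pill type. Staff blinded to pill type should apply the rule identically to both arms.
- If the case report forms do not already do so, record pill taken (yes or no) and time at the start of each of the first 18 sessions. Reconcile the blister pack after session 18 and not at a fixed Week 3: since "patients are permitted up to 8 weeks to complete these 36 treatment sessions", session 18 falls at week 18/6 = 3 on schedule but at week 18/4.5 = 4 at the slowest even pace (36/8 = 4.5 sessions per week).
- Report pills taken and the pill-to-TR interval by arm. Show the Aim 2 per-protocol result with and without the pill criterion, and keep intent-to-treat primary.

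The cost is a short amendment, one brief daily item and one blister-pack field if these are not already in place, a smaller per-protocol set (raw-scale standard error up about 8% or 14% if 3 or 5 per arm are lost from 22), and possible selection imbalance if tolerability differs.
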